12.3 Methods for Evaluation of Measurable Disease

All measurements should be taken and recorded in metric notation using a ruler or calipers. All baseline evaluations should be performed as closely as possible to the beginning of treatment and never more than 4 weeks before the beginning of the treatment.

The same method of assessment and the same technique should be used to characterize each identified and reported lesion at baseline and during follow-up. Imaging-based evaluation is preferred to evaluation by clinical examination unless the lesion(s) being followed cannot be imaged but are assessable by clinical exam.

Clinical lesions: Clinical lesions will only be considered measurable when they are superficial (e.g., skin nodules and palpable lymph nodes) and ≥ 10 mm diameter as assessed using calipers (e.g., skin nodules). In the case of skin lesions, documentation by color photography, including a ruler to estimate the size of the lesion, is recommended.

Chest x-ray: Lesions on chest x-ray are acceptable as measurable lesions when they are clearly defined and surrounded by aerated lung. However, CT is preferable.

Conventional CT and MRI: This guideline has defined measurability of lesions on CT scan based on the assumption that CT slice thickness is 5 mm or less. If CT scans have slice thickness greater than 5 mm, the minimum size for a measurable lesion should be twice the slice thickness. MRI is also acceptable in certain situations (e.g. for body scans).

Use of MRI remains a complex issue. MRI has excellent contrast, spatial, and temporal resolution; however, there are many image acquisition variables involved in MRI, which greatly impact image quality, lesion conspicuity, and measurement. Furthermore, the availability of MRI is variable globally. As with CT, if an MRI is performed, the technical specifications of the scanning sequences used should be optimized for the evaluation of the type and site of disease. Furthermore, as with CT, the modality used at follow-up should be the same as was used at baseline and the lesions should be measured/assessed on the same pulse sequence. It is beyond the scope of the RECIST guidelines to prescribe specific MRI pulse sequence parameters for all scanners, body parts, and diseases. Ideally, the same type of scanner should be used and the image acquisition protocol should be followed as closely as possible to prior scans. Body scans should be performed with breath-hold scanning techniques, if possible.

PET-CT: At present, the low dose or attenuation correction CT portion of a combined PET-CT is not always of optimal diagnostic CT quality for use with RECIST measurements. However, if the site can document that the CT performed as part of a PET-CT is of identical diagnostic quality to a diagnostic CT (with IV and oral contrast), then the CT portion of the PET-CT can be used for RECIST measurements and can be used interchangeably with conventional CT in accurately measuring cancer lesions over time. Note, however, that the PET portion of the CT introduces additional data which may bias an investigator if it is not routinely or serially performed.

Ultrasound: Ultrasound is not useful in assessment of lesion size and should not be used as a method of measurement. Ultrasound examinations cannot be reproduced in their entirety for independent review at a later date and, because they are operator dependent, it cannot be guaranteed that the same technique and measurements will be taken from one assessment to the next. If new lesions are identified by ultrasound in the course of the study, confirmation by CT or MRI is advised. If there is concern about radiation exposure at CT, MRI may be used instead of CT in selected instances.

Endoscopy, Laparoscopy: The utilization of these techniques for objective tumor evaluation is not advised. However, such techniques may be useful to confirm complete pathological response when biopsies are obtained or to determine relapse in trials where recurrence following complete response (CR) or surgical resection is an endpoint.

Tumor markers: Tumor markers alone cannot be used to assess response. If markers are initially above the upper normal limit, they must normalize for a patient to be considered in complete clinical response. Specific guidelines for both CA-125 response (in recurrent ovarian cancer) and PSA response (in recurrent prostate cancer) have been published [JNCI 96:487-488, 2004; J Clin Oncol 17, 3461-3467, 1999; J Clin Oncol 26:1148-1159, 2008]. In addition, the Gynecologic Cancer Intergroup has developed CA-125 progression criteria which are to be integrated with objective tumor assessment for use in first-line trials in ovarian cancer [JNCI 92:1534-1535, 2000].

Cytology, Histology: These techniques can be used to differentiate between partial responses (PR) and complete responses (CR) in rare cases (e.g., residual lesions in tumor types, such as germ cell tumors, where known residual benign tumors can remain).

The cytological confirmation of the neoplastic origin of any effusion that appears or worsens during treatment when the measurable tumor has met criteria for response or stable disease is mandatory to differentiate between response or stable disease (an effusion may be a side effect of the treatment) and progressive disease.

FDG-PET: While FDG-PET response assessments need additional study, it is sometimes reasonable to incorporate the use of FDG-PET scanning to complement CT scanning in assessment of progression (particularly possible 'new' disease). New lesions on the basis of FDG-PET imaging can be identified according to the following algorithm:

- Negative FDG-PET at baseline, with a positive FDG-PET at follow-up is a sign of PD based on a new lesion.
- No FDG-PET at baseline and a positive FDG-PET at follow-up: If the positive FDG-PET at follow-up corresponds to a new site of disease confirmed by CT, this is PD. If the positive FDG-PET at follow-up is not confirmed as a new site of disease on CT, additional follow-up CT scans are needed to determine if there is truly progression occurring at that site (if so, the date of PD will be the date of the initial abnormal FDG-PET scan). If the positive FDG-PET at follow-up corresponds to a pre-existing site of disease on CT that is not progressing on the

basis of the anatomic images, this is not PD.

- FDG-PET may be used to upgrade a response to a CR in a manner similar to a biopsy in cases where a residual radiographic abnormality is thought to represent fibrosis or scarring. The use of FDG-PET in this circumstance should be prospectively described in the protocol and supported by disease-specific medical literature for the indication. However, it must be acknowledged that both approaches may lead to false positive CR due to limitations of FDG-PET and biopsy resolution/sensitivity.

Note: A 'positive' FDG-PET scan lesion means one which is FDG avid with an uptake greater than twice that of the surrounding tissue on the attenuation corrected image.

12.4 Response Criteria

12.4.1 Evaluation of Target Lesions

Complete Response (CR): Disappearance of all target lesions. Any pathological lymph nodes (whether target or non-target) must have reduction in short axis to <10 mm.

Partial Response (PR): At least a 30% decrease in the sum of the diameters of target lesions, taking as reference the baseline sum diameters.

Progressive Disease (PD): At least a 20% increase in the sum of the diameters of target lesions, taking as reference the smallest sum on study (this includes the baseline sum if that is the smallest on study). In addition to the relative increase of 20%, the sum must also demonstrate an absolute increase of at least 5 mm. (Note: the appearance of one or more new lesions is also considered progressions).

Stable Disease (SD): Neither sufficient shrinkage to qualify for PR nor sufficient increase to qualify for PD, taking as reference the smallest sum diameters while on study.

12.4.2 Evaluation of Non-Target Lesions

Complete Response (CR): Disappearance of all non-target lesions and normalization of tumor marker level. All lymph nodes must be non-pathological in size (<10 mm short axis).

Note: If tumor markers are initially above the upper normal limit, they must normalize for a patient to be considered in complete clinical response.

Non-CR/Non-PD: Persistence of one or more non-target lesion(s) and/or maintenance of tumor marker level above the normal limits.

Progressive Disease (PD): Appearance of one or more new lesions and/or

unequivocal progression of existing non-target lesions. Unequivocal progression should not normally trump target lesion status. It must be representative of overall disease status change, not a single lesion increase.

Although a clear progression of “non-target” lesions only is exceptional, the opinion of the treating physician should prevail in such circumstances, and the progression status should be confirmed at a later time by the review panel (or Principal Investigator).

12.4.3 Evaluation of Best Overall Response

The best overall response is the best response recorded from the start of the treatment until disease progression/recurrence (taking as reference for progressive disease the smallest measurements recorded since the treatment started). The patient's best response assignment will depend on the achievement of both measurement and confirmation criteria.

For Patients with Measurable Disease (i.e., Target Disease)

Target Lesions	Non-Target Lesions	New Lesions	Overall Response	Best Overall Response when Confirmation is Required*
CR	CR	No	CR	>4 wks. Confirmation**
CR	Non-CR/Non-PD	No	PR	>4 wks. Confirmation**
CR	Not evaluated	No	PR	
PR	Non-CR/Non-PD/not evaluated	No	PR	
SD	Non-CR/Non-PD/not evaluated	No	SD	Documented at least once >4 wks. from baseline**
PD	Any	Yes or No	PD	no prior SD, PR or CR
Any	PD***	Yes or No	PD	
Any	Any	Yes	PD	

* See RECIST 1.1 manuscript for further details on what is evidence of a new lesion.

** Only for non-randomized trials with response as primary endpoint.

*** In exceptional circumstances, unequivocal progression in non-target lesions may be accepted as disease progression.

Note: Patients with a global deterioration of health status requiring discontinuation of treatment without objective evidence of disease progression at that time should be reported as “symptomatic deterioration.” Every effort should be made to document the objective progression even after discontinuation of treatment.

For Patients with Non-Measurable Disease (i.e., Non-Target Disease)

Non-Target Lesions	New Lesions	Overall Response
CR	No	CR
Non-CR/non-PD	No	Non-CR/non-PD*
Not all evaluated	No	not evaluated
Unequivocal PD	Yes or No	PD
Any	Yes	PD
* 'Non-CR/non-PD' is preferred over 'stable disease' for non-target disease since SD is increasingly used as an endpoint for assessment of efficacy in some trials so to assign this category when no lesions can be measured is not advised		

12.4.4 Duration of Response

Duration of overall response: The duration of overall response is measured from the time measurement criteria are met for CR or PR (whichever is first recorded) until the first date that recurrent or progressive disease is objectively documented (taking as reference for progressive disease the smallest measurements recorded since the treatment started).

The duration of overall CR is measured from the time measurement criteria are first met for CR until the first date that progressive disease is objectively documented.

Duration of disease control (CR, PR, stable disease): Disease control is measured from the start of the treatment until the criteria for progression are met, taking as reference the smallest measurements recorded since the treatment started, including the baseline measurements.

12.4.5 Efficacy

Efficacy will be measured by the overall response rate (CR+PR) defined by RECIST criteria and by time to progression.

12.4.6 Progression-Free Survival

Progression-free survival is defined as the duration of time from start of treatment to time of progression or death, whichever occurs first.

12.4.7 Overall Survival

Overall survival is measured from time of diagnosis to time of death.

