Based on the evidence presented, we propose a phase I/II trial to test our hypotheses that the addition of PD 0332991 to cetuximab will be feasible and will improve tumor response rate and time-to-progression (TTP) in patients with platin-resistant incurable SCCHN in comparison to historical controls. In the phase II portion of the trial, patients will be required to have HPV-unrelated SCCHN tumors (which as a group are known to have nearly universal cyclin D1 overexpression or amplification and/or p16 loss) to enrich the likelihood of clinical benefit of PD 0332991. Cetuximab will be used as the platform to add PD 0332991 to since cetuximab is the current standard FDA-approved treatment indicated for patients with platin-resistant incurable SCCHN.

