2.2 Secondary Objectives

1. Phases I and II, Arms 1, 2, and 3: To assess the adverse events of PD 0332991 in combination with cetuximab
2. Phase II, Arms 1, 2, and 3: To assess the progression-free survival (PFS) of patients with incurable SCCHN treated with PD 0332991 in combination with cetuximab
3. Phase II, Arms 1, 2, and 3: To assess the overall survival (OS) of patients with incurable SCCHN treated with PD 0332991 in combination with cetuximab
4. Phase II, Arms 1, 2, and 3: To assess duration of response/stable disease of patients with incurable HPV-unrelated SCCHN treated with PD 0332991 in combination with cetuximab

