3.0 PATIENT SELECTION

3.1 Inclusion Criteria

1. Histologically or cytologically confirmed diagnosis of squamous cell carcinoma of the head and neck.
2. Disease must be considered incurable. Incurable is defined as metastatic disease or a local or regional recurrence in a previously irradiated site that is unresectable (or patient declines resection).
3. Measurable disease defined as lesions that can be accurately measured in at least one dimension (longest diameter to be recorded) as ≥ 10 mm with CT scan, as ≥ 20 mm by

- chest x-ray, or ≥ 10 mm with calipers by clinical exam. (Phase I only: patients without measurable disease by RECIST 1.1 criteria but with evaluable disease by imaging or physical exam will be eligible as well.)
4. Phase I only: any (or no) prior therapy for metastatic disease is allowed, including cetuximab. If a patient has not received prior standard therapy, s/he must have been offered and refused prior standard therapy.
 5. Phase II only:
Arm 1: disease progression after at least one cycle of prior treatment with cisplatin or carboplatin for incurable disease. Prior treatment with cetuximab for incurable disease is not permitted.
Arms 2 and 3: disease progression after at least one cycle of treatment with cetuximab for incurable disease.
 6. Phase II only: at least one line of prior therapy for incurable disease.
 7. Phase II only:
Arms 1 and 2: disease must be determined to be HPV-unrelated. HPV-unrelated SCCHN is defined as either p16-negative OPSCC or non-OPSCC (larynx, hypopharynx, oral cavity) or p16-negative unknown primary SCC presenting with a level 2 or 3 neck node. p16 will be assessed by IHC; a specimen showing any staining will be considered p16-positive.
Arm 3: disease must be HPV-related SCCHN (defined as OPSCC or unknown primary presenting with a neck mass that is either p16 positive or HPV ISH or PCR positive).
 8. Minimum of 14 days elapsed since the end of any prior therapy.
 9. At least 18 years of age.
 10. Resolution of all acute toxic effects of prior anti-cancer therapy or surgical procedures to NCI CTCAE version 4.0 Grade ≤ 1 (except alopecia or other toxicities not considered a safety risk for the patient at investigator's discretion)
 11. ECOG performance status ≤ 2 (see Appendix A).
 12. Adequate bone marrow and organ function as defined below:
 - a. Absolute neutrophil count $\geq 1,500$ mm³
 - b. Platelets $\geq 100,000$ mm³
 - c. Hemoglobin > 9 g/dL

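### Overall survival is timed from an unspecified diagnosis instead of the start of study treatment, so it counts survival that eligibility guarantees and is biased upward

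*Combined protocol and SAP*

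**What the plan says.** The whole definition, in Section 12.4.7, is: "Overall survival is measured from time of diagnosis to time of death". It does not say whether this means first diagnosis of the cancer, diagnosis of recurrence or metastasis, or diagnosis of incurable disease. No other section redefines the endpoint. Section 15.0 gives no analysis method for overall survival, so it supplies neither another time origin nor an allowance for time before enrolment.

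The neighbouring endpoints use a different clock:

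- Section 12.4.6: "Progression-free survival is defined as the duration of time from start of treatment to time of progression or death".
- Section 12.4.4: "Disease control is measured from the start of the treatment until the criteria for progression are met".

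The objective served, in Section 2.2 and for Phase II Arms 1, 2 and 3, is: "To assess the overall survival (OS) of patients with incurable SCCHN treated with PD 0332991 in combination with cetuximab". Section 2.3 also plans to correlate molecular changes with overall survival, among other endpoints, in Arms 1 and 2.

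Section 3.1 fixes what must have happened before enrolment:

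- All of Phase II: "Phase II only: at least one line of prior therapy for incurable disease".
- "Arm 1: disease progression after at least one cycle of prior treatment with cisplatin or carboplatin for incurable disease".
- "Arms 2 and 3: disease progression after at least one cycle of treatment with cetuximab for incurable disease".
- At least 14 days must have passed since prior therapy ended.

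**The concern.** The objective is survival in patients given the combination. A clock that starts at diagnosis adds an interval before the combination was given, and a patient who died in that interval could not have enrolled. This is immortal time, and it can only lengthen the result.

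Three things are at stake:

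- The secondary survival estimate in each Phase II arm would be too favourable as an account of the combination.
- Overall survival and progression-free survival would run on different clocks, so the reported difference between them would have no clear meaning. Arms with different lengths of prior treatment would not be comparable on overall survival either.
- The exploratory correlations in Section 2.3 would use an outcome that partly measures history before enrolment.

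**Working it through.** **No figure to reproduce.** The documents state no expected median, survival rate, event count or power for overall survival. The check is therefore one of definition and direction, followed by an illustration.

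**Step 1: does diagnosis precede study treatment?** Section 3.1 requires a prior line for incurable disease, progression after at least one cycle of platin (Arm 1) or cetuximab (Arms 2 and 3), and at least 14 days since prior therapy. Diagnosis of the cancer, or of incurable disease, must come before all of that. For every Phase II patient the interval therefore exceeds 14 days plus one prior cycle (cycle length not stated). Its actual length is not given.

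**Step 2: direction and exact size on the mean.** Let T be the time from start of study treatment to death, and G the time from diagnosis to start of study treatment, with G > 0.

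- Overall survival as defined = G + T.
- With complete follow-up, mean(G + T) − mean(T) = mean(G), whatever the survival distribution.

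This is an identity and needs no simulation. Only the size of G is unknown.

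**Step 3: illustration with a fixed gap.** All inputs are assumptions: T is exponential with median m, and every patient has the same gap g. Then

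- median overall survival = g + m;
- 12-month survival = 2^(−(12 − g)/m) if g < 12, and 1 if g ≥ 12.

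| Gap g (months) | m = 6: median | m = 6: 12-month rate | m = 9: median | m = 9: 12-month rate |
|---|---|---|---|---|
| 0 (from treatment) | 6 | 2^(−2) = 25% | 9 | 2^(−12/9) = 40% |
| 1.5 | 7.5 | 2^(−10.5/6) = 30% | 10.5 | 2^(−10.5/9) = 45% |
| 3 | 9 | 2^(−9/6) = 35% | 12 | 2^(−9/9) = 50% |
| 6 | 12 | 2^(−6/6) = 50% | 15 | 2^(−6/9) = 63% |
| 12 | 18 | 100% | 21 | 100% |
| 24 | 30 | 100% | 33 | 100% |

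**Step 4: variable gap.** The 100% entries arise only because every patient is given the same gap of at least 12 months. With a lognormal gap (median 12 months, log-SD 0.6, both assumed), simulation gives 12-month survival of 82% for m = 6 and 87% for m = 9, with medians of about 20.3 and 23.7 months. With a gap median of 24 months the rates are 97% and 98%.

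**Step 5: with censoring.** Kaplan-Meier estimates were run on 100,000 simulated patients per scenario, with exponential survival, a lognormal gap (log-SD 0.5), uniform censoring at 6 to 60 months and no delayed entry. For an assumed true median of 8 months:

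| Gap median (months) | Median from diagnosis | 12-month survival from diagnosis (from treatment: about 0.35) |
|---|---|---|
| 1.5 | 9.7 | 0.41 |
| 6 | 15.2 | 0.64 |
| 12 | 22.3 | 0.87 |
| 24 | 35.5 | 0.99 |

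Across true medians of 5, 8 and 11 months and these four gaps (12 scenarios), the median was overstated in every one, by about 1.7 to 28 months.

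**The case against.** **Survival from diagnosis is a legitimate quantity.** It is, but it is not the objective in Section 2.2. Even as survival from diagnosis, an ordinary Kaplan-Meier estimate would be too high, because patients come under observation only if they survive to enrol. No delayed-entry adjustment is planned.

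**The wording may be a template slip, and analysts could use the treatment date.** That date is already needed for progression-free survival, so the problem can be corrected at analysis without new data. But nothing in the documents tells the analyst to do so, and following the stated rule gives the biased result.

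**The size may be small.** This stands as a caution. If diagnosis means diagnosis of incurable disease, a gap of about 1 to 1.5 months is possible, and 12-month survival would move only from 25% to 30%, or from 40% to 45%, under the assumptions above. The large shifts need long gaps, and the 100% rates need a fixed gap. None of this changes the direction.

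**Little depends on overall survival.** This also stands. Section 12.4.5 measures efficacy by response rate and time to progression. The historical-control hypothesis in Section 1.7 is that the addition "will improve tumor response rate and time-to-progression (TTP) in patients with platin-resistant incurable SCCHN in comparison to historical controls". The decision and stopping rules in Section 15.0 use response and toxicity.

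**Conclusion.** The concern holds. As written, overall survival includes time before study treatment that every Phase II patient had to survive in order to enrol. As an estimate of survival in patients treated with the combination, it is biased upward. The direction follows from Sections 12.4.7 and 3.1 alone, as does the excess in the mean, which equals the mean diagnosis-to-treatment interval under complete follow-up. How large that interval is cannot be found from the documents, and every numerical illustration rests on assumed medians and gaps.

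The consequence is confined to the secondary survival estimate in Arms 1 to 3 and the exploratory correlations with overall survival in Arms 1 and 2. The primary response-rate analysis, the sample sizes (30, 30 and 24) and the stopping rules are unaffected. It should be fixed, but it does not threaten the trial's main conclusion.

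**What to change.** Replace the sentence in Section 12.4.7 with: *Overall survival is measured from the start of study treatment to death from any cause; patients not known to have died are censored at the date last known alive.*

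If survival from diagnosis is also wanted, name the diagnosis, label the analysis supplementary and use delayed entry (left truncation) at the start of study treatment. With 24 to 30 patients per arm the early risk sets could be very small and the estimate unstable. The method also assumes that entry time is independent of survival. Both limits should be stated.

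No new data are needed: Section 12.4.6 already requires the treatment start date, and Sections 5.10 and 10.0 already provide for survival checks every 2 months for 5 years. The cost is a protocol modification, which Section 16.0 requires to be sent to the secondary sites and their local IRBs. Reported overall survival will be shorter.
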